### **5.2.2.2.8 Radiation Therapy Adverse Events**

The descriptions and grading scales found in the revised NCI Common Terminology Criteria for Adverse Events (CTCAE), version 4.0 will be utilized for grading all adverse events. Placement of a feeding tube should be recorded as adverse event “use of a feeding tube during and after treatment” (e.g., greater than or less than 50% of nutrition by tube). Other common radiation adverse events include: fatigue, weight loss, regional alopecia, xerostomia, hoarseness, transient ear discomfort, and skin erythema and desquamation within the treatment fields. Less common long-term treatment adverse events include: hypothyroidism, loss of hearing, chronic swallowing dysfunction requiring permanent feeding tube, and skin/soft tissue fibrosis. Much less common radiation adverse events include: mandibular osteoradionecrosis, and cervical myelopathy (< 1% with restriction of spinal cord dose to max dose of 45 Gy).

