## **5.7 Subject Withdrawal/Discontinuation Criteria**

Subjects may withdraw consent at any time for any reason or be dropped from the trial at the discretion of the investigator should any untoward effect occur. In addition, a subject may be withdrawn by the investigator or the Sponsor if enrollment into the trial is inappropriate, the trial plan is violated, or for administrative and/or other safety reasons. Specific details regarding discontinuation or withdrawal are provided in Section 7.1.4 – Other Procedures.

A subject must be discontinued from the trial for any of the following reasons:

- The subject or legal representative (such as a parent or legal guardian) withdraws consent.
- Confirmed radiographic disease progression
- Unacceptable adverse experiences as described in Section 5.2.1.2

- Intercurrent illness that prevents further administration of treatment
- Investigator's decision to withdraw the subject
- The subject has a confirmed positive serum pregnancy test
- Noncompliance with trial treatment or procedure requirements
- The subject is lost to follow-up
- Administrative reasons

The End of Treatment and Follow-up visit procedures are listed in Section 6 (Protocol Flow Chart) and Section 7.1.5 (Visit Requirements). After the end of treatment, each subject will be followed for 30 days for adverse event monitoring (serious adverse events will be collected for 90 days after the end of treatment as described in Section 7.2.3.1). Subjects who discontinue for reasons other than progressive disease will have post-treatment follow-up for disease status until disease progression, initiating a non-study cancer treatment, withdrawing consent or becoming lost to follow-up. After documented disease progression each subject may be followed by telephone or in person for overall survival until death, withdrawal of consent, or the end of the study, whichever occurs first.

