##### **7.1.2.6.2 Post-Treatment Assessment Imaging**

Twelve weeks (+/- 2 weeks) after completion of last radiation treatment (week 19 on flow chart), a PET/CT or CT of neck and chest should be performed to assess for early relapse. Patients will be followed clinically for recurrence after initial post-treatment imaging. No

further imaging is required after initial assessment unless there is suspicion of relapsed disease.

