#### **7.1.5.3 Post-Treatment Visits**

##### **7.1.5.3.1 Safety Follow-Up Visit**

If subjects do not discontinue or withdraw early:

- The mandatory Safety Follow-up Visit should correspond to approximately a week after the post-treatment imaging (week 19) on week 20's End of Treatment/Discontinuation visit.

If subjects discontinue or withdraw early:

- The mandatory Safety Follow-Up Visit should be conducted approximately 30 days after the last dose of trial treatment or before the initiation of a new anti-cancer treatment, whichever comes first.

For all subjects, all AEs that occur prior to the Safety Follow-Up Visit should be recorded. Subjects with an AE of Grade > 1 will be followed until the resolution of the AE to Grade 0-1 or until the beginning of a new anti-neoplastic therapy, whichever occurs first. SAEs that occur within 90 days of the end of treatment or before initiation of a new anti-cancer treatment should also be followed and recorded.

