### **7.2 Assessing and Recording Adverse Events**

An adverse event is defined as any untoward medical occurrence in a patient or clinical investigation subject administered a pharmaceutical product and which does not necessarily have to have a causal relationship with this treatment. An adverse event can therefore be any unfavorable and unintended sign (including an abnormal laboratory finding, for example), symptom, or disease temporally associated with the use of a medicinal product or protocol-specified procedure, whether or not considered related to the medicinal product or protocol-specified procedure. Any worsening (i.e., any clinically significant adverse change in frequency and/or intensity) of a preexisting condition that is temporally associated with the use of Merck's product, is also an adverse event.

Changes resulting from normal growth and development that do not vary significantly in frequency or severity from expected levels are not to be considered adverse events. Examples of this may include, but are not limited to, teething, typical crying in infants and children and onset of menses or menopause occurring at a physiologically appropriate time.

Merck product includes any pharmaceutical product, biological product, device, diagnostic agent or protocol-specified procedure, whether investigational (including placebo or active comparator medication) or marketed, manufactured by, licensed by, provided by or distributed by Merck for human use.

Adverse events may occur during the course of the use of Merck product in clinical trials or within the follow-up period specified by the protocol, or prescribed in clinical practice, from overdose (whether accidental or intentional), from abuse and from withdrawal.

Adverse events may also occur in screened subjects during any pre-allocation baseline period as a result of a protocol-specified intervention, including washout or discontinuation of usual therapy, diet, placebo treatment or a procedure.

Progression of the cancer under study is not considered an adverse event unless it is considered to be drug related by the investigator.

All adverse events will be recorded from the time the consent form is signed through 30 days following cessation of treatment and at each examination on the Adverse Event case report forms/worksheets. The reporting timeframe for adverse events meeting any serious criteria is described in section 7.2.3.1.

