If any adverse events related to study drug, pembrolizumab continue after the 30 days post treatment, they should be followed until resolution and/or if they are ongoing at the end of the follow up period, they should continue to be followed per standard of care per their MD.

New SAE/AE's are to be collected and documented in the study EDC during follow up (past 30 days following cessation of treatment) only if they are found to be related to study drug, pembrolizumab.

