### **7.2.3 Immediate Reporting of Adverse Events to the Sponsor and to Merck**

#### **7.2.3.1 Serious Adverse Events**

A serious adverse event is any adverse event occurring at any dose or during any use of Merck's product that:

- Results in death;
- Is life threatening;
- Results in persistent or significant disability/incapacity;
- Results in or prolongs an existing inpatient hospitalization;
- Is a congenital anomaly/birth defect;
- Is a new cancer (that is not a condition of the study);
- Is associated with an overdose;
- Is another important medical event

Refer to Table 6 for additional details regarding each of the above criteria.

Any serious adverse event, or follow up to a serious adverse event, including death due to any cause other than progression of the cancer under study that occurs to any subject from the time the consent is signed through 90 days following cessation of treatment, or the initiation of new anti-cancer therapy, whichever is earlier, whether or not related to Merck product, must be reported within 24 hours to the Sponsor and within 2 working days to Merck Global Safety.

Non-serious Events of Clinical Interest will be forwarded to Merck Global Safety and will be handled in the same manner as SAEs.

Additionally, any serious adverse event, considered by an investigator who is a qualified UCCI-HN-15-01 Amendment 17

18MAR2021

physician to be related to Merck product that is brought to the attention of the investigator at any time outside of the time period specified in the previous paragraph also must be reported immediately to the Sponsor and to Merck.

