#### **7.2.3.2 Events of Clinical Interest**

Selected non-serious and serious adverse events are also known as Events of Clinical Interest (ECI). ECIs identified from the date of first dose through 90 days following cessation of treatment, or 30 days after the initiation of a new anticancer therapy, whichever is earlier, must be recorded as such on the Adverse Event case report forms/worksheets and reported within 24 hours to the Sponsor and within 2 working days to Merck Global Safety (Attn: Worldwide Product Safety; [contact]) regardless of attribution to study treatment, consistent with standard SAE reporting guidelines. Events of clinical interest for this trial include:

1. An overdose of Merck product, as defined in Section 7.2.1 - Definition of an Overdose for This Protocol and Reporting of Overdose to the Sponsor, that is not associated with clinical symptoms or abnormal laboratory results.
2. An elevated AST or ALT lab value that is greater than or equal to 3X the upper limit of normal and an elevated total bilirubin lab value that is greater than or equal to 2X the upper limit of normal and, at the same time, an alkaline phosphatase lab value that is less than 2X the upper limit of normal, as determined by way of protocol-specified laboratory testing or unscheduled laboratory testing.\*

**\*Note:** These criteria are based upon available regulatory guidance documents. The purpose of the criteria is to specify a threshold of abnormal hepatic tests that may require an additional evaluation for an underlying etiology. The trial site guidance for assessment and follow up of these criteria can be found in the Investigator Trial File Binder (or equivalent).

1. Additional adverse events:

Subjects should be assessed for possible ECIs prior to each dose. Lab results should be evaluated and subjects should be asked for signs and symptoms suggestive of an immune-related event. Subjects who develop an ECI thought to be immune-related should have additional testing to rule out other etiologic causes. If lab results or symptoms indicate a possible immune-related ECI, then additional testing should be performed to rule out other etiologic causes. If no other cause is found, then it is assumed to be immune-related.

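### Section 7.2 keeps SAEs judged unrelated to pembrolizumab out of the EDC from day 31, while Sections 5.7, 7.1.5.3.1 and 7.2.3.1 cover all SAEs to day 90

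*Combined protocol and SAP*

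**What the plan says.** Section 7.2 records all adverse events from consent to 30 days after treatment stops. For serious events it refers the reader elsewhere: "The reporting timeframe for adverse events meeting any serious criteria is described in section 7.2.3.1". Its closing paragraph then sets a separate rule for later follow-up. That rule restricts the collection of new SAEs and AEs: they are "documented in the study EDC during follow up (past 30 days following cessation of treatment) only if they are found to be related to" pembrolizumab. SAEs are named explicitly in that rule.

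Three other sections deal with SAEs over the same period:

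- Section 5.7: "serious adverse events will be collected for 90 days after the end of treatment", with a reference to Section 7.2.3.1.
- Section 7.1.5.3.1: SAEs "within 90 days of the end of treatment or before initiation of a new anti-cancer treatment should also be followed and recorded".
- Section 7.2.3.1: SAEs are reported to the sponsor within 24 hours, from consent "through 90 days following cessation of treatment, or the initiation of new anti-cancer therapy, whichever is earlier, whether or not related to Merck product".

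Events of clinical interest have their own rule in Section 7.2.3.2. Through day 90, or 30 days after new anticancer therapy if that is earlier, they "must be recorded as such on the Adverse Event case report forms/worksheets", whatever their attribution.

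**The concern.** For days 31 to 90, Section 7.2 filters SAEs by relationship to pembrolizumab, and the other sections do not. A site reading Section 7.2 straight through is sent to Section 7.2.3.1 for the SAE timeframe and is then told to leave some of those same SAEs out of the EDC.

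The first primary objective (Section 3.1) is the frequency and severity of side effects of pembrolizumab given with radiation or with chemoradiation. Sections 8.1.1 and 8.2.1 define the safety endpoints as all adverse events of grades 1 to 5, and Section 8.2.4.1 compares grade 3 and 4 rates with historical targets of 39% and 50%. None of these is limited to pembrolizumab-related events. The events filtered out are those attributed to something else, including the radiation, cisplatin or surgery that make up the rest of the treatment. Table 6 in Section 7.2.4 offers only a yes or no on relationship to pembrolizumab. A late event that could have several causes can therefore be scored as no and dropped.

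Section 5.2.2.2.8 shows the type of event at stake: "Less common long-term treatment adverse events include: hypothyroidism, loss of hearing, chronic swallowing dysfunction requiring permanent feeding tube". A new serious event of this kind, attributed to radiation, would be reported but not entered. Section 10.6.1 names OnCore and/or RedCap as the study database, and nothing in the documents describes bringing sponsor-held SAE reports into it. A safety table run from the database could therefore make the combination look less toxic than it was.

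**Working it through.** The plan states no figure to reproduce. The check compares the rules side by side and then sizes the affected period.

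**Rules applied to one case.** Take an SAE on day 50 after treatment stops, judged due to radiation, with no new anti-cancer therapy started.

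| Section | What it requires | Causality limit? | Result for this SAE |
|---|---|---|---|
| 5.7 | Collection for 90 days | No | Collected |
| 7.1.5.3.1 | Following and recording for 90 days, or until new anti-cancer treatment | No | Recorded |
| 7.2.3.1 | Report to sponsor through day 90, or until new therapy if earlier | Expressly none | Reported |
| 7.2, closing paragraph | Collection and EDC entry after day 30 | Pembrolizumab-related only | Not entered |

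The limit based on new anti-cancer therapy in two of these sections is not a causality limit, so it does not remove the conflict. Reporting under Section 7.2.3.1 can coexist with the EDC rule. The incompatibility lies in what is collected and recorded.

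**Post-treatment period affected.** 90 − 30 = 60 days, and 60/90 = 67% of the post-treatment SAE window.

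**Share of the full SAE window, consent to day 90.** The inputs come from the flow chart in Section 6.1, in days relative to surgery. Treatment is assumed to stop with the planned pembrolizumab dose at adjuvant week 16.

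- Consent: day −35 to day −7.
- Adjuvant week 1: day 28 to day 77.
- Week 16 is 15 weeks later, which is 105 days: 28 + 105 = 133 to 77 + 105 = 182.
- Ninety days after that: 133 + 90 = 223 to 182 + 90 = 272.
- Window length: 223 + 7 = 230 to 272 + 35 = 307 days.
- Share: 60/307 = 19.5% to 60/230 = 26.1%.

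**Timing relative to radiation.** Section 7.1.2.6.2 places the scan twelve weeks after the last fraction at week 19, so radiation ends at about week 19 − 12 = 7.

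- Days 31 to 90 after a week 16 dose: 16 + 31/7 = 20.4 to 16 + 90/7 = 28.9 weeks.
- Time since radiation: 20.4 − 7 = 13.4 to 28.9 − 7 = 21.9 weeks.

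**Sensitivity to when the clock starts.** The flow chart footnotes and Section 7.1.5.3.1 attach end of treatment to the week 20 visit. Counting from week 20 adds 4 weeks, or 28 days. The window becomes 258 to 335 days, the share 60/335 = 17.9% to 60/258 = 23.3%, and the affected period 17.4 to 25.9 weeks after radiation. The 60 days in conflict do not change.

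**The case against.** The strongest reply is that the rules can be followed together. Sections 5.7 and 7.1.5.3.1 do not name the EDC. Section 5.7 takes its meaning from Section 7.2.3.1, which is a reporting rule, so its collection requirement might be met by the sponsor report. Sites would then report every SAE to day 90 and enter only the related ones. This does not fully work. Section 7.2 restricts collection as well as entry, and collection is what Section 5.7 requires. The requirement in Section 7.1.5.3.1 to record these SAEs stands beside its general instruction to record adverse events, and it would go unmet. Section 5.4.1 also expects concomitant medications given more than 30 days after the last dose to be recorded for SAEs without regard to cause. A drug could then be recorded for an SAE that is itself absent from the EDC.

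Several points on consequence do stand:

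- The sponsor receives these SAEs within 24 hours, and under Section 10.6.2 the DSMB receives explanations of SAEs and the frequency and severity of adverse events. Expedited reporting does not depend on the EDC rule.
- A Clinical Monitoring Plan is kept on file and is not in these documents, so a reconciliation step may exist there. No passage says that the safety analysis uses the EDC alone.
- Only new events are excluded. Swallowing trouble that began during radiation is already on record and followed. The late-radiation example applies only to a new serious event.
- Some SAEs unrelated to pembrolizumab would also be unrelated to radiation or cisplatin. Leaving those out would not understate toxicity of the combination.

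These points limit how many events could be lost. They do not reconcile the rules.

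**Conclusion.** The contradiction holds. Followed as written, the closing paragraph of Section 7.2 keeps out of the study database SAEs that Sections 5.7 and 7.1.5.3.1 require to be collected and recorded and that Section 7.2.3.1 requires to be reported. The conflict covers days 31 to 90, or a shorter period if new anti-cancer therapy starts first. The calendar shares rest on the planned schedule and on the week 16 dose as the end of treatment; moving the clock to week 20 changes them only modestly.

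Calendar time is not event count. The documents give no late SAE rate, so the undercount cannot be sized, and it reaches the analysis only if the safety tables are drawn from the EDC without reconciliation. In that case the direction is toward under-reporting toxicity, and the EDC would not match the SAE reports. Related SAEs, events of clinical interest, the lead-in dose-limiting toxicity rule and expedited reporting are unaffected. The point should be fixed because it touches a primary objective and the plan already contains the rule that resolves it.

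**What to change.** Amend the closing paragraph of Section 7.2 so that:

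- the related-only rule applies after day 30 to non-serious adverse events;
- it applies to SAEs only after the window in Section 7.2.3.1 has closed (90 days, or new anti-cancer therapy if earlier);
- all SAEs inside that window are entered in the EDC and included in the safety analysis, whatever their attribution;
- events of clinical interest continue to follow the recording rule in Section 7.2.3.2.

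The cost is a short protocol amendment and a small amount of EDC entry for events that must already reach the sponsor within 24 hours. The document is already at Amendment 17, so SAEs left out under the current wording would also have to be entered retrospectively from the sponsor's reports. The documents do not say how many there are. No treatment or clinical management rule changes.

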### **7.2.1 Definition of an Overdose for This Protocol and Reporting of Overdose to the Sponsor and to Merck**

For purposes of this trial, an overdose of Pembrolizumab will be defined as any dose of 1,000 mg or greater ( $\geq 5$  times the indicated dose). No specific information is available on the treatment of overdose of Pembrolizumab. Appropriate supportive treatment should be provided if clinically indicated. In the event of overdose, the subject should be observed closely for signs of toxicity. Appropriate supportive treatment should be provided if clinically indicated.

If an adverse event(s) is associated with ("results from") the overdose of a Merck product, the adverse event(s) is reported as a serious adverse event, even if no other seriousness criteria are met.

If a dose of Merck's product meeting the protocol definition of overdose is taken without any associated clinical symptoms or abnormal laboratory results, the overdose is reported as a non-serious Event of Clinical Interest (ECI), using the terminology "accidental or intentional overdose without adverse effect."

All reports of overdose with and without an adverse event must be reported within 24 hours to the Sponsor and within 2 working days hours to Merck Global Safety. (Attn: Worldwide Product Safety; [contact])

### **7.2.2 Reporting of Pregnancy and Lactation to the Sponsor and to Merck**

Although pregnancy and lactation are not considered adverse events, it is the responsibility of investigators or their designees to report any pregnancy or lactation in a subject (spontaneously reported to them), including the pregnancy of a male subject's female partner that occurs during the trial or within 120 days of completing the trial completing the trial, or 30 days following cessation of treatment if the subject initiates new anticancer therapy, whichever is earlier. All subjects and female partners of male subjects who become pregnant must be followed to the completion/termination of the pregnancy. Pregnancy outcomes of spontaneous abortion, missed abortion, benign hydatidiform mole, blighted ovum, fetal death, intrauterine death, miscarriage and stillbirth must be reported as serious events (Important Medical Events). If the pregnancy continues to term, the outcome (health of infant) must also be reported.

Such events must be reported within 24 hours to the Sponsor and within 2 working days to Merck Global Safety. (Attn: Worldwide Product Safety; [contact])

### **7.2.3 Immediate Reporting of Adverse Events to the Sponsor and to Merck**

#### **7.2.3.1 Serious Adverse Events**

A serious adverse event is any adverse event occurring at any dose or during any use of Merck's product that:

- Results in death;
- Is life threatening;
- Results in persistent or significant disability/incapacity;
- Results in or prolongs an existing inpatient hospitalization;
- Is a congenital anomaly/birth defect;
- Is a new cancer (that is not a condition of the study);
- Is associated with an overdose;
- Is another important medical event

Refer to Table 6 for additional details regarding each of the above criteria.

Any serious adverse event, or follow up to a serious adverse event, including death due to any cause other than progression of the cancer under study that occurs to any subject from the time the consent is signed through 90 days following cessation of treatment, or the initiation of new anti-cancer therapy, whichever is earlier, whether or not related to Merck product, must be reported within 24 hours to the Sponsor and within 2 working days to Merck Global Safety.

Non-serious Events of Clinical Interest will be forwarded to Merck Global Safety and will be handled in the same manner as SAEs.

Additionally, any serious adverse event, considered by an investigator who is a qualified UCCI-HN-15-01 Amendment 17

18MAR2021

physician to be related to Merck product that is brought to the attention of the investigator at any time outside of the time period specified in the previous paragraph also must be reported immediately to the Sponsor and to Merck.

